3. OBJECTIVES

Our primary objectives are to:

- Describe the epidemiology, clinical presentation, bleeding score, bleeding episodes, quality of life, laboratory parameters, genetics and treatment of *homozygous* and known *heterozygous* individuals (of all ages) with rare bleeding disorders (disorders of fibrinogen, FII, FV, FV & VIII, FVII, FX, FXI, FXIII, alpha-2-antiplasmin and PAI-1 deficiency) in the Netherlands;
- Examine the relationship between the clinical and laboratory presentation (clinical and laboratory phenotype), and between phenotypes and genetics (genotype);
- Examine the relationship between quality of life, phenotype and genotype;
- ~~Validate the established factor activity levels for patients to remain without symptoms.~~

Our secondary objectives are to:

- Validate the established factor activity levels for patients to remain without symptoms.
- Compare the clinical presentation, bleeding score, quality of life and laboratory parameters of individuals with a rare bleeding disorder (disorders of fibrinogen, FII, FV, FV & VIII, FVII, FX, FXI, FXIII, alpha-2-antiplasmin and PAI-1 deficiency) to those of individuals with haemophilia A or B in cooperation with the HIN-6 investigators
- Establish a firm base for a future Dutch registry for *homozygous* and known *heterozygous* individuals with rare bleeding disorders
 - To develop a standard set of patient-reported, clinical and administrative data to be collected on a regular basis
- Liaise with the pro-RBDD study, a similar study in Italy, to work towards a pan-European study linking phenotype to genotype in individuals with rare bleeding disorders
- To assess if the NHA can distinguish mild clinical phenotypes in patients with similar factor activity levels
- To evaluate the usefulness of saliva coagulation biomarker tests in the management of patients with a rare bleeding disorder
- To examine whether age-dependent laboratory changes in factor concentrations and fibrinolysis occur in individuals with rare bleeding disorders and if so, whether they influence clinical phenotype
- To evaluate if patients with rare bleeding disorders are protected from arterial thrombosis

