TSH	Thyroid Stimulating Hormone
VWF	Von Willebrand Factor
Wbp	Personal Data Protection Act (in Dutch: Wet Bescherming Persoonsgegevens)
WES	Whole Exome Sequencing
WMO	Medical Research Involving Human Subjects Act (in Dutch: Wet Medisch-wetenschappelijk Onderzoek met Mensen)

SUMMARY

Rationale: Rare bleeding disorders (deficiency of fibrinogen, factor II, V, V&VIII, VII, X, XI, XIII, α 2-antiplasmin or plasminogen activator inhibitor 1) are not well defined with respect to their clinical phenotype, laboratory phenotype en genotype. At present, little is known about their clinical presentation, bleeding scores, bleeding episodes, health-related quality of life, laboratory parameters, genetics and current treatment. There are large differences in bleeding tendency and weak correlations with the level of factor deficiencies. Therefore, it is essential to perform thorough research in patients with rare bleeding disorders and perform laboratory and genetic tests, to seek explanations for the variety in clinical phenotype.

Objective: The purpose of the RBiN study is to describe the epidemiology, bleeding tendency, laboratory parameters, quality of life and genetics of all known patients in the Netherlands with rare bleeding disorders. In addition, the study aims to examine the relationship between clinical phenotype, laboratory phenotype and genotype.

Study design: cross-sectional multicenter observational study.

Study population: all patients registered in Dutch Haemophilia Treatment Centers with known disorders of the coagulation factors fibrinogen, factor II, V, V & VIII, VII, X, XI, XIII, α 2-antiplasmin and plasminogen activator inhibitor type 1, aged 1 years and older.

Main study parameters/endpoints:

Description of the clinical phenotype, laboratory phenotype, genotype and quality of life.

Nature and extent of the burden and risks associated with participation, benefit and group relatedness: participating patients will be invited for one visit to their treatment center in order to draw blood, take a saliva sample and perform questionnaires. This will take approximately 40 to 120 minutes. Since the population of patients with RBDs is very small it is important to include all patients, also minors (children <18 years), in the study (around one third of known patients are minors). Therefore, this study may be regarded as group-related. The risk associated with participation is negligible.

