FXI deficiency can be inherited autosomal recessive and autosomal dominant[33]. It is the mildest of the rare bleeding disorders, with bruising, epistaxis and menorrhagia as the most common manifestations [5, 14]. The correlation between coagulation factor activity and clinical bleeding is poor [19]. This may (in part) be explained by the coexistence of other coagulation disorders. In some patients with severe FXI deficiency a combined FXI and von Willebrand disease has been reported, leading to a more severe bleeding tendency [16]. Excessive bleeding has also been reported in heterozygous individuals. A single study from the United Kingdom showed that 48% of heterozygous individuals had a bleeding tendency, [34]. Comparison of histories between partially deficient and non-deficient individuals demonstrated a higher prevalence of menstrual problems (41% vs. 18%), an increase in significant bruising (38% vs. 14%), an increased likelihood of excessive bleeding after dental extractions (51% vs. 9%), and an increased number of blood transfusions after interventions (56% vs. 0%). Bleeding in heterozygous individuals has also been described to be related to genetically compound disease, other factor deficiencies or defects, or platelet dysfunction in some cases [12-18].

FXIII deficiency

FXIII deficiency is an autosomal recessive disorder. This deficiency has serious clinical consequences. Of 112 cases reported in the literature from 1978 23 individuals (21%) had died of bleeding, and notably 22 of these were relatives of established cases, for whom the diagnosis was highly likely but could not be proven [35]. Umbilical cord bleeding was seen in

73-80% of cases and may be delayed up to 19 days after birth; surgical bleeding in 84%; superficial bruising in 58-60%; subcutaneous haematomas in 55-58%; intracranial bleeding in 25-30%; mouth and gum bleeding 30-48%; muscle bleeding 27%; and joint bleeding in 24-55% of reported cases [35, 36]. Habitual abortions (50% of women) and menorrhagia (35% of women) are also frequent. Women with a complete deficiency are unable to carry a pregnancy to term [36, 37]. Impaired wound healing is another symptom patients may experience [37]. It is currently not clear if people with a heterozygous factor XIII deficiency have an increased bleeding risk[38].

Alpha-2-antiplasmin deficiency

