4. STUDY DESIGN

RBiN is a cross-sectional observational study. All participants will be asked to fill out questionnaires, will be interviewed, and asked to provide blood and saliva samples. The blood samples will be used for analyses and to set up a biobank.

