6. METHODS

6.1. Study procedures

Patients will be approached by their own treating physician. Data will be collected through questionnaires, a clinical interview, a blood and saliva sample obtained from each participant, and thorough review of electronic patient records. An overview of study procedures is given in Table 4. All procedures are study related. In case a physician visit with the treating physician is already planned, or in case a venepuncture for regular diagnostics or treatment is already planned, this can be combined with the study procedures to prevent an extra visit.

Table 4 Overview of study procedures for each adult subject

Procedure	Outcome
Study physician visit	

 Clinical interview 	
 Bleeding score (ISTH-BAT) RBD bleeding score[52] Children: iCHEC
Questionnaires	

 Self-administered 	
 Demographic characteristics (generic) Socio-economic characteristics (generic) Clinical characteristics (bleeds, treatment), HIV status (patients born before 1985) and hepatitis C status (patients born before 1992) Medical history (generic) Sexuality (generic) General health status (Rand-36/Cho-KLAT) Sports and physical activity (MAQ/HeptestQ) Adherence (VERITAS-pro) Pain (generic) Needle phobia (generic) Experience with care (generic)
Electronic patient records	
	
 Date of birth Sex Baseline factor activity level Baseline factor antigen level Treatment type (prophylactic treatment or on-demand treatment) Body weight and height Bleeding score at diagnosis Relevant previous medical history, i.e. arterial thrombosis, atherosclerosis, medication use, pregnancies and outcomes
Blood samples: 72-83 ml	

 Haemostasis 	
 Screening tests - PFA - Haemoglobin

		
 - Thrombocytes - VWF ristocetin cofactor - VWF antigen - VWF collagen binding assay - FVIII act one stage - FVIII chromogen - aPTT - PT - Fibrinogen - Thrombin time 	
 - Leucocytes & differentiation - Peripheral blood smear - Creatinine - ALAT - TSH - D-dimer - Antitrombin - Protein C - Protein S - TFPI
	
 • Diagnostic tests 	
 - FII - FV - FVII - FIX 	
 - FX - FXI - FXII - FXIII

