6.5. Follow-up of subjects withdrawn from treatment

Not applicable as this study has no follow-up.

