7. STATISTICAL ANALYSIS

Statistical analysis will be performed by the research team at Radboud university medical center. First we describe the general outline of statistical analyses, then we discuss specific statistical procedures for the primary and secondary objectives separately, if appropriate.

In general, continuous variables will be described using standard summary statistics (e.g. mean, medians and corresponding 95% confidence interval (CI),); categorical variables will be described using frequencies and percentages with their 95% CIs. Group differences will be determined using analysis of variance (ANOVA) or Student's t-test for continuous variables and Fisher's exact test for categorical variables (Fisher-Freeman-Halton exact test for variables with more than two categories). Non-parametric tests will be used for results with non-normal distributions. Two-sided p-values smaller than 0.05 will be considered statistically significant. Because of the explorative character of this study no correction for multiple testing will be applied.

The following parameters will be categorized when appropriate:

- Bleeding score (ISTH-BAT): ≥ 5 abnormal for women, ≥ 3 abnormal for men
- Clinical bleeding severity [19]:
 - Asymptomatic: no documented bleeding episodes
 - Grade I bleeding: bleeding that occurred after trauma or drug ingestion (antiplatelet or anticoagulation therapy)
 - Grade II bleeding: spontaneous minor bleeding (bruising, ecchymoses, minor wounds, oral cavity bleeding, epistaxis and menorrhagia)
 - Grade III bleeding: spontaneous major bleeding (intramuscular haematomas requiring hospitalizations, haemarthrosis, bleeding of the central nervous system, the umbilical cord or the gastrointestinal tract)

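### The ageing objective asks about change with age, but section 7.2 only compares different people at one visit and names no bleeding measure for the clinical half

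*Combined protocol and SAP*

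**What the plan says.** - **Objective.** Section 3 (secondary objectives) includes "To examine whether age-dependent laboratory changes in factor concentrations and fibrinolysis occur in individuals with rare bleeding disorders" and goes on to ask whether they influence clinical phenotype.
- **Design.** Section 4: "RBiN is a cross-sectional observational study". The Summary says "participating patients will be invited for one visit to their treatment center", and section 6.5 says "Not applicable as this study has no follow-up".
- **Analysis.** Section 7.2 plans descriptive statistics and one regression. Age is the dependent variable and factor activity the independent variable, with adjustment for age at data collection, sex and unlisted further covariates. No fibrinolysis marker, bleeding measure, disorder, zygosity or age at diagnosis is named.
- **Bleeding severity.** Section 2 equates clinical phenotype with clinical bleeding severity. The grade in section 7 has no time window. Its lowest level is the absence of any documented bleed, and its highest includes "haemarthrosis, bleeding of the central nervous system, the umbilical cord or the gastrointestinal tract".
- **Earlier values.** Table 4 (section 6.1) takes "Baseline factor activity level", the matching antigen level and "Bleeding score at diagnosis" from patient records. It lists date of birth but no date for any of these values and no date of diagnosis. Section 7 never sets them against the visit values.

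**The concern.** With one visit, an age gradient is a difference between people who happen to be known at different ages. It equals change within a person only if young and old known patients are otherwise alike. The protocol gives reasons to doubt that:

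- Sections 1 and 1.1 say less severe cases are under-reported, and section 1.2 warns of ascertainment bias in record-based data.
- Section 5.1 expects known heterozygotes to be a more severe subset. It counts about 179 of them against an estimated 93,000 to 99,000.
- Section 1.2 ties bleeding in FV deficiency, and in heterozygous alpha-2-antiplasmin deficiency, largely to surgery, trauma, delivery or dental extraction. Such challenges accumulate with age, so milder patients may become known later.
- Severe patients may be lost early. For FXIII, section 1.2 reports that "23 individuals (21%) had died of bleeding" among 112 published cases.

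Both mechanisms raise the average level among older known patients. They could produce a rise that is not ageing, or mask a fall. Section 1.2 says levels in alpha-2-antiplasmin deficiency decline with age and symptoms may increase. With 29 known patients, that decline could be hidden.

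The clinical half has a separate gap, because no bleeding outcome is specified. If the section 7 grade were used and read as covering the whole lifetime, a newborn cord bleed would fix a patient at grade III for good. Section 1.7 frames the question around whether bleeding eases as levels rise, and such a grade could not show that.

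**Working it through.** The plan gives no sample size, effect size or power for this objective, so there is no figure to reproduce. The calculations test whether the mechanism works and in which direction.

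**1. Two-class arithmetic, with no true change with age.** Assumed: 30% severe at 5% activity, 70% mild at 40%, and a fraction *k* of mild patients already known when young. By old age all mild patients are known and 21% of severe patients have been lost (0.30 × 0.79 = 0.237). The 21% is borrowed from the FXIII collection as a deliberately large value.

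- Young mean = (0.3 × 5 + 0.7 × *k* × 40) / (0.3 + 0.7 × *k*)
- Old mean = (0.237 × 5 + 0.7 × 40) / 0.937 = 29.185 / 0.937 = 31.1

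| *k* | Young mean | Old minus young |
|---|---|---|
| 1 | 29.5 / 1 = 29.5 | +1.6 |
| 0.75 | 22.5 / 0.825 = 27.3 | +3.9 |
| 0.5 | 15.5 / 0.65 = 23.8 | +7.3 |

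Within a class the difference is 5 − 5 = 0 or 40 − 40 = 0. In this model the whole gradient comes from the changing mix of classes.

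**2. Simulation, with no true change with age.** 1000 runs per setting, n = 236 (0.70 × 337 = 235.9, from section 5.1). Assumed: ages uniform from 1 to 80; one third severe (5%, SD 3) and two thirds mild (45%, SD 12); assay CV 10%; mean age at diagnosis 2 years if severe and 10 to 30 if mild; excess mortality in severe patients 0 to 0.01 per year.

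| Setting | Cross-sectional slope, points per decade | Runs with p < 0.05 |
|---|---|---|
| No selection | about 0 | 6% |
| Late diagnosis of mild patients only | +0.7 to +1.6 | 18% to 66% |
| Late diagnosis plus excess mortality 0.005 to 0.01 | +1.0 to +2.4 | 37% to 96% |

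Over the same settings, within-patient change from diagnosis to visit averaged −0.004 to +0.003 points per decade, significant in 4% to 6% of runs. That assumes an unselected earlier value and the same assay both times.

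**3. A lifetime grade.** With a constant grade III hazard (assumed 0.03 per year if severe, 0.01 if mild), the proportion who have ever had grade III rose 6 to 8 percentage points per decade, significant in at least 98% of runs at n = 236. On that reading the measure rises with age even when the bleeding rate does not.

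**4. Room for analysis by disorder.** The detectable correlation at 80% power and two-sided 0.05 is tanh[(1.96 + 0.84)/√(n − 3)]. This gives 0.18 for n = 236, 0.35 for FXI (0.70 × 88 ≈ 62) and 0.89 for FX (0.70 × 10 = 7).

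**The case against.** **The sizes are assumptions.** This stands. Nothing in the documents supports *k* = 0.75 or 0.5. About one third of known patients are minors (Summary, section 8.4), whereas uniform ages from 1 to 80 put only 17/79 = 22% under 18. The calculations show possibility and direction only.

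**The survival evidence is thin.** This also stands. The FXIII collection dates from 1978, and 22 of the 23 deaths were relatives whose diagnosis could not be proven. FXIII is 16 of 337 known patients, while FVII and FXI together are 180, and section 1.2 calls FXI deficiency the mildest of these disorders. Selective recognition is the better-supported route.

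**The section 7 grade is not the stated outcome here.** A reader might infer that the plan relates age to a lifetime-worst grade. Section 7.2 names no bleeding variable for this objective, section 7 states no worst-ever rule, and Table 4 also collects ISTH-BAT, the RBD score, iCHEC and questionnaire bleeds. The questionnaires are separate documents, so their recall windows cannot be seen. What stands is that the outcome is unspecified and the one graded scale has no time window.

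**Stratification may be enough.** In the two-class model it removes the bias entirely. In practice levels vary within a class and recognition may depend on them, so it should reduce the bias but need not remove it. Zygosity is also largely unknown at present (Table 3 note). Exome sequencing could supply it, but section 6.2 gives two different lower age limits, 12 and 16, which need reconciling.

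**A paired analysis has its own biases.** This stands, and it is why pairing should not be primary. Baseline is undefined and might mean an untreated level rather than an earlier one. A low diagnostic value regresses to the mean, and section 2 calls many assays highly variable. The instrument for the diagnosis score is not stated. Adjusting for continuous calendar era would defeat the analysis. With an assumed two-year visit window (variance 4/12 = 0.33) and a baseline-date SD of 10 years, the correlation of elapsed time with baseline date is −100 / (10 × √100.33) = −0.998, a variance inflation factor of about 300.

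**Conclusion.** The point holds as a mismatch between question and analysis. Section 3 asks about change, section 7.2 offers a between-person comparison at one visit, and the selective recognition described in the background is not carried into it. An age gradient could therefore appear, or be hidden, with no change in any patient. The size in this study is unknown; the figures above (+1.6 to +7.3 points, or +0.7 to +2.4 per decade) rest on assumed class mix, ascertainment and mortality. The clinical half has no specified outcome.

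A reader might go further and conclude that the objective cannot be answered as designed. The documents do not support that. Analysis within disorder and zygosity deals with the main mechanism illustrated, and a cross-sectional age difference can be reported as such. Nor do they establish that usable within-patient data already exist, given an undefined and undated baseline.

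This is a secondary objective in a study declared exploratory, but the repair is cheap and changes what can be concluded. Separately, section 7.2 makes age both the outcome and an adjustment covariate. Turning the model round is needed, but would still leave a comparison between people.

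**What to change.** 1. **Cross-sectional analysis (7.2).** Make factor level the outcome and age the predictor, within disorder and zygosity (with an unknown category), adjusted for age at diagnosis and sex. Report a cross-sectional age difference, not a change, including for fibrinolysis markers with no earlier value.
2. **CRF.** Define baseline. During the planned record review, capture the date of diagnosis, the date and laboratory of the baseline factor level, and the date and instrument of the diagnosis bleeding score.
3. **Supportive within-patient analysis.** Relate untreated visit level minus baseline level to years elapsed, by disorder. Use a confirmatory value rather than the first diagnostic one where recorded. Restrict to comparable assays, or add a sensitivity analysis by assay, and do not adjust for continuous calendar era.
4. **Clinical half.** Name the outcome: bleeding in a fixed recent window, or score accrued since diagnosis where the same instrument was used both times.

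The cost is a handful of fields in a record review already planned, plus wording in 7.2. The downsides are incomplete or non-comparable historical values, regression to the mean, assay drift, and low precision in the rarer disorders, where results will be descriptive. These are why the paired analysis should be supportive and not primary.

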4. STUDY DESIGN

RBiN is a cross-sectional observational study. All participants will be asked to fill out questionnaires, will be interviewed, and asked to provide blood and saliva samples. The blood samples will be used for analyses and to set up a biobank.

5. STUDY POPULATION

5.1. Population (base)

Based on the prevalence in the general population of 1:500,000 to 1 per 2 million persons [1, 2], and a total population of 17 million, there should be 129 to 145 individuals with a homozygous rare bleeding disorder in the Netherlands. This could be higher taking into account the possible influences of high-risk populations such as Ashkenazi or Iraqi Jews with high FXI deficiency rates. To date, 337 patients with a rare bleeding disorder are known to the eight Dutch centers that treat such patients. Approximately one third of these patients are homozygous; and around two thirds are heterozygous individuals.¹

All known homozygous and heterozygous patients with a rare bleeding disorder will be invited to participate.

Heterozygous prevalence in the Netherlands have not been evaluated, but can be calculated according to the Hardy-Weinberg principle² to be 93,000 to 99,000 persons, or 0.55% to 0.58% of the Dutch population (5.5 to 5.8 per 1,000 persons) for all rare bleeding disorders combined. Though the estimated number of heterozygous persons in the Netherlands is much higher than the number of persons known to one of the eight treating centers (~179 heterozygous patients³), we expect that the individuals with a known heterozygosity represent a subset with a more severe clinical presentation, who are therefore of interest to our research question.

Characteristics of the Dutch source population

The characteristics of the Dutch population (both homozygous and heterozygous) are largely unknown and are a part of this study. Numbers of known patients per rare bleeding disorder are presented in

[Table 3](#)

[Table 3.](#)

¹ A quick inventory in the Radboud university medical center learned that two thirds of patients were heterozygous individuals whereas one third were homozygous individuals. Based on an inventory of 63 medical files performed on July 8, 2016: 65% missing information, 24% heterozygosity, 11% homozygosity

² The Hardy-Weinberg proportion stipulates that for a single locus with two alleles denoted 'A' and 'a' with population frequencies p and q respectively, the expected genotype frequencies are p² for the AA homozygous individuals, q² for the aa homozygous individuals, and 2pq for the heterozygous individuals. The sum of these frequencies must be 1, thus p² + 2pq + q² = 1 and p + q=1.

Table 3 Prevalence of rare bleeding disorders in the Netherlands

Deficiency	Estimated prevalence homozygosity in general population as described in the literature [1, 2]	Estimated prevalence homozygosity in the Dutch general population	Patients known at present in the Netherlands (homozygous/heterozygous/unknown)
Fibrinogen	1:1 million	17	28
II	1:2 million	9	9
V	1:1 million	17	22
V & VIII	1:1-2 million	9-17	4
VII	1:500,000	34	92
X	1:1 million	17	10
XI	1:1 million	17	88
XIII	1:1-2 million	9-17	16
PAI-1	Unknown	Unknown	39
Alpha-2-antiplasmin	Unknown	Unknown	29
	Total	129-145	337

Abbreviations: CI: confidence interval

\$ Based on a population figure of 17,024,133 (www.cbs.nl/nl-nl/visualisaties/bevolkingsteller)

* Based on a quick inventory of participating sites, which are all sites in the Netherlands licensed to treat rare bleeding disorders. Homozygosity or heterozygosity largely unknown

Willingness of patients to participate

We expect that a high proportion of patients with rare bleeding disorders are willing to participate in RBiN. Patients are aware of the rarity of their disorder and the lack of research. The Netherlands Hemophilia Society (Nederlandse Vereniging van Hemofilie Patiënten, NVHP) is a co-initiator of RBiN and a patient representative takes seat in the steering committee. Based on the response rate of the HiN studies we expect a (similar) response rate of 70% [51].

